9.7.1.6.1 PRIMARY EFFICACY ANALYSIS

E2027 is planned for use as a symptomatic treatment in subjects with DLB. The treatment effect of E2027 may be confounded by the use of rescue medications during the study. For the purposes of statistical analysis, rescue medications are defined as medications for treatment of symptoms of DLB that are prohibited or restricted (as specified in [Section 9.4.7.2](#)) and they are not used in accordance with the rules in [Section 9.4.7.2](#).

This confounding may mask the true treatment effect of E2027 in treating subjects with DLB. The treatment effect of interest will be the efficacy as measured by coprimary endpoints that

would be observed at 12 weeks without initiation or dose change of any prohibited or restricted medications as mentioned above regardless of whether or when the assigned treatment was discontinued due to adverse event, lack of efficacy or any other events related to treatment or study outcome. The target population (DLB subjects) is defined by inclusion/exclusion criteria.

There are 2 coprimary efficacy endpoints, change from baseline in the MoCA total score at 12 weeks and CIBIC-Plus scale at 12 weeks. Overall, there are 2 null hypotheses (H_0) to be tested in the primary analysis:

- H_{01} : There is no difference in the mean change from baseline in the MoCA total score at 12 weeks between E2027 and placebo.
- H_{02} : The proportional odds ratio based on CIBIC-Plus scale at 12 weeks between E2027 and placebo is equal to 1.

The corresponding 2 alternative hypotheses are that there is a difference in the mean change from baseline in MoCA total score at 12 weeks in this coprimary endpoint between E2027 and placebo and the proportional odds ratio based on CIBIC-Plus scale at 12 weeks between E2027 and placebo is not equal to 1.

The study will be considered positive if statistically significant improvement is observed in both coprimary endpoints in the E2027 treatment group.

The change from baseline of MoCA total score for E2027 compared to placebo will be analysed using the approach proposed by [Mehrotra, et al. \(2017\)](#) with slight modification based on reasons for missing. The following is a list of the missing reasons and their missing mechanisms:

- Data not observed because of dropouts due to AEs, lack of efficacy or any other events related to treatment or study outcome will be considered as missing not at random (MNAR).
- The effect had rescue medication not been made available to subjects prior to Week 12 is not observable for subjects who initiated prohibited or restricted rescue medication. For these subjects, the data collected after initiation of prohibited rescue medication are assumed to contain no treatment effect in the E2027 treatment group. Technically, response data collected after initiation of prohibited rescue medication will be treated as MNAR such that response data as MNAR in the E2027 treatment group would be imputed by the mean response in the placebo treatment group as described by the imputation method below.
- Data not observed because of dropouts due to intercurrent events definitely not related to treatment or outcome (eg, withdraw consent due to logistical problems) will be considered as missing at random (MAR). All events will be classified unambiguously in the statistical analysis plan.

The mean of missing endpoint values in the E2027 treatment group considered as MAR would be imputed using the mean of missing endpoint values of completers in the E2027 treatment

group and the mean of missing endpoint values in E2027 treatment group considered as MNAR will be imputed by the mean of the overall endpoint distribution under placebo based on the above missing reasons and the corresponding missing mechanisms. The mean of the overall endpoint distribution under placebo will be obtained using mixed effects model of repeated measures (MMRM) within the placebo group assuming MAR. Test statistics and the *P*-value will be obtained as described by [Mehrotra, et al. \(2017\)](#).

The sensitivity analysis for MoCA will be a tipping point analysis based on control-based mean imputation proposed by [Mehrotra, et al. \(2017\)](#) in the same article, which is an increasingly more conservative means such that the *P*-value is equal to the pre-specified alpha (0.025 [1-sided]). Drug benefit is interpreted as convincing if the tipping point is worse than the mean placebo dropouts. Additional sensitivity analysis for different classification of missing mechanism (ie, all missing data will be considered as MNAR regardless of reason of dropouts), will be provided.

In order to generate inputs for proposed primary and sensitivity analyses, a MMRM will be used for the E2027 group completers, placebo group completers, and all placebo group subjects. The model will be adjusted for baseline MoCA, visit (Weeks 6 and 12), randomization stratification variable (receiving AChEI or not; geographical region [North America, Europe, Japan]), and baseline MoCA × visit as fixed effects. An unstructured covariance matrix will be used to model the covariance of within subject effect. The values of baseline MoCA will be adjusted using the overall baseline mean of all study subjects in computing LS-means.

The primary analysis of CIBIC-Plus scale at 12 weeks will be based on control-based pattern imputation at subject level ([Yuan 2014](#)). The CIBIC-Plus scale at 12 weeks will be imputed as an ordinal response variable. The same missing reasons and corresponding missing mechanism as in the analysis of change from baseline in MoCA total score will be used in this analysis. Only the missing ordinal responses in E2027 treatment group considered as MNAR will be imputed by ordinal responses observed in the placebo group using a pattern-mixture model approach under MNAR assumption. Other missing ordinal responses will be imputed assuming MAR. The CIBIC-Plus scale at 12 weeks (observed or imputed) will be analysed using proportional odds model, a special case of generalized linear mixed models (GLMM), in multiply imputed data sets. The results obtained from all multiply imputed data sets will be combined for overall inference using Rubin's rules. The GLMM model will include treatment, randomization stratification variables (receiving AChEI or not; geographical region [North America, Europe, Japan]) as fixed effects. The model will be fitted using GLMM with a multinomial distribution and a cumulative logit link function. The proportional odds ratio estimate between E2027 and placebo, the corresponding 95% CI, and *P*-values will be presented.

The sensitivity analysis for CIBIC-Plus scale will be a tipping point analysis based on multiple imputation at subject level using pattern mixture model approach ([Yuan, 2014](#)), which is based on an increasingly more conservative shift parameter (based on cumulative logit function values for CIBIC-Plus scale) such that the *P*-value is equal to the pre-specified alpha (0.05 [2-sided]). Additional sensitivity analysis for different classification of missing

mechanism (ie, all missing data will be considered as MNAR regardless of reason of dropouts), will be provided.

If the proportional odds assumption is contradicted by the observed data in either entire population or any stratum, the GLMM method will be replaced by the non-parametric van Elteren test in both primary analysis and sensitivity analysis. The CIBIC-Plus scale at 12 weeks will be analysed using van Elteren test adjusting 2 randomization stratification variables (receiving AChEI or not; geographical region [North America, Europe, Japan]). The null hypothesis corresponding to the van Elteren test is that there is no difference in the location of distribution of CIBIC-Plus scale at 12 weeks between E2027 and placebo. The corresponding alternative hypothesis is that there is a difference in the location of distribution of CIBIC-Plus scale at 12 weeks between E2027 and placebo.

The potential effect of baseline MMSE on the primary result will be evaluated as an additional covariate in the primary model as appropriate. Subgroup (eg, region, age group, baseline AChEI status, baseline MMSE group, and baseline memantine status) analyses will be performed as appropriate. (revised per Amendment 03)

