9.7.1.6 Efficacy Analyses

The significance level for all efficacy endpoint analyses is 0.05 (2-sided), unless otherwise stated, with no adjustments for multiplicity. The efficacy analyses will be performed on the FAS except per protocol analysis will be performed on the PPS.

Baseline for the primary and secondary efficacy endpoints is defined as the last pretreatment assessment. An additional baseline, based on the mean of all prerandomization values at the Screening and Baseline assessment, will be explored due to assess potential prerandomization variability.

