#### **Sensitivity Analysis of Change from Baseline in the MoCA Total Score at 12 Weeks for non-EMA registration**

A sensitivity analysis will be produced to repeat the primary analysis for MoCA but to censor data after changes in AChEI medications.

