#### **Supplementary Analysis for both non-EMA and EMA registrations**

Subgroup (eg, region, age group, baseline AChEI status, baseline memantine status, and baseline MMSE subgroup) analyses will be performed for the subgroups defined in Section 5.3.4. The treatment effect within each subgroup and corresponding 95% CI for each co-primary endpoint will be summarized and also depicted using forest plot.

The treatment effect will be also examined using PP Analysis Set for each co-primary endpoint and analysis.

Descriptive statistics and graphical presentation for each co-primary endpoint will be provided.

Table 4 Primary Efficacy Analyses			
Score		Analysis for non-EMA Registration	Analysis for EMA Registration
MoCA	Primary	MMRM	Control based mean imputation with Mehrotra

	Sensitivity	As primary, but censor changes in AChEI medication	As primary, but censor changes in AChEI medication
	Supplementary	As primary, subgroups	As primary, subgroups
		As primary, Per Protocol Analysis Set	As primary, Per Protocol Analysis Set
CIBIC-Plus	Primary	GLMM	Proportional odds model with control-based pattern imputation
	Sensitivity	Censor changes in both AChEI and non-AChEI medications	Censor changes in both AChEI and non-AChEI medications
		Exclude subjects with changes/new AChEI and non-AChEI restricted medications	Exclude subjects with changes/new AChEI and non-AChEI restricted medications
	Supplementary	As primary, subgroups	As primary, subgroups
		As primary, Per Protocol Analysis Set	As primary, Per Protocol Analysis Set

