## 7 CHANGES IN THE PLANNED ANALYSES

Due to correspondence with the FDA during the study, the primary analyses for the non-EMA registrations were changed during the study to use MMRM for continuous efficacy data and GLMM for categorical efficacy data. The pre-planned analyses were kept for EMA registration, based on pre-study scientific advice from the EMA. The overall change was the ordering of importance of these analyses for each specific registration.

The co-primary analyses of MoCA and CIBIC-Plus will not be censored based on changes in the AChEI and non-AChEI restricted medications. This is based on review of blinded data which showed no improvement on efficacy after the use of this medication. As a sensitivity analysis, changes in AChEI restricted medications will be censored for MoCA and changes in either AChEI or non-AChEI restricted medications will be censored for CIBIC-Plus. The censoring differs based on the clinical interpretation that CIBIC-Plus measures aspects that could change with changes in the non-AChEI restricted medications.

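### The SAP omits, without naming them, the tipping-point and all-missing-as-MNAR analyses that the protocol promises for MoCA and CIBIC-Plus, so no analysis goes beyond the placebo assumption for dropouts

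*Protocol*

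**What the plan says.** **Protocol (Synopsis, Statistical Methods; Section 9.7.1.6.1).** Each co-primary has two missing-data sensitivity analyses.

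- MoCA: "The sensitivity analysis for MoCA will be a tipping point analysis based on control-based mean imputation". The protocol adds a reading rule: benefit counts as convincing if the tipping point is worse than the mean of the placebo dropouts.
- CIBIC-Plus: "The sensitivity analysis for CIBIC-Plus scale will be a tipping point analysis based on multiple imputation at subject level", using a shift on the cumulative logit scale.
- Both: a further run in which "all missing data will be considered as MNAR regardless of reason of dropouts".

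**SAP Section 5.4.1 and Table 4.** The only sensitivity analyses concern medication changes. For MoCA (non-EMA), "A sensitivity analysis will be produced to repeat the primary analysis for MoCA but to censor data after changes in AChEI medications". The Table 4 entry for both registrations is "As primary, but censor changes in AChEI medication". For CIBIC-Plus, data are censored after AChEI or non-AChEI changes, or subjects with such changes are excluded.

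**SAP Section 5.4.2 and Table 5.** Each registration's primary method for the two co-primaries is repeated as an additional secondary analysis for the other registration, with and without data collected after treatment discontinuation.

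**SAP Section 7.** It says the pre-planned analyses were kept for EMA, and then: "The overall change was the ordering of importance of these analyses for each specific registration". The version 4 summary of changes says only that supplementary analyses were reduced, to make the co-primary analyses easier to interpret.

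**The concern.** The SAP has two primary approaches. The non-EMA one (MMRM, GLMM) relies on MAR. The EMA one sorts missing values by reason: those classed MNAR in the E2027 arm take the placebo mean or placebo pattern, and the rest are handled as MAR. The protocol's two sensitivity analyses were aimed at the weak points of the second approach. The tipping point asks how much worse than placebo the E2027 dropouts would have to be before significance is lost. The all-MNAR run removes any dependence on how reasons were sorted.

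That sorting involves judgement. The protocol says the SAP will classify all events without ambiguity. The primary discontinuation reasons in Protocol Section 9.5.5 include loss to follow-up, subject choice and other, and the SAP's EMA MoCA section does not assign these by name to either class.

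If the trial were positive, the protocol's own criterion for convincing MoCA benefit could not be evaluated from the outputs the SAP plans.

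**Working it through.** **1. Presence or absence (this decides the point).**

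| Analysis | Protocol | SAP |
|---|---|---|
| Tipping point, MoCA | Yes | No |
| Tipping point, CIBIC-Plus | Yes | No |
| All missing as MNAR, both endpoints | Yes | No |
| Control-based imputation, both endpoints | Primary | EMA primary; non-EMA additional secondary |
| MMRM/GLMM, both endpoints | Not as a comparative analysis | Non-EMA primary; EMA additional secondary |
| Data after medication change as MNAR | Within the primary | EMA sensitivity |

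In the SAP, no row sets E2027 dropouts worse than placebo, and no row moves dropouts classed MAR into MNAR.

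**2. The plan's own figure.** 80 completers per arm at 12% dropout: 80 / (1 - 0.12) = 90.9, so 91 per arm and 182 in total. This reproduces.

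**3. Illustration for MoCA.** Let d be the difference among completers, m the fraction of E2027 values missing at Week 12, and k the distance of the E2027 dropouts' mean below the placebo mean. The estimate is then (1 - m)d - mk. I assume placebo dropouts average the placebo mean.

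Inputs from SAP Section 4: SD 3, d = 1.4, 80 completers per arm, m = 0.12.

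- SE = 3 x sqrt(2/80) = 0.474; critical difference 1.96 x 0.474 = 0.930.
- All dropouts classed MAR: estimate 1.40. All classed MNAR (k = 0): 0.88 x 1.4 = 1.232. The classification can therefore move the estimate by up to 0.17.
- Tipping point with SE held fixed: (1.232 - 0.930) / 0.12 = 2.5 points below the placebo mean.
- Tipping point with SE scaled by 0.88 (critical difference 0.818): (1.232 - 0.818) / 0.12 = 3.4 to 3.5.

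Inputs from Protocol Section 9.7.2: SD 1.3, d = 0.6.

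- SE = 1.3 x sqrt(2/80) = 0.206; critical difference 0.403, or 0.355 scaled.
- All MNAR: 0.88 x 0.6 = 0.528.
- Tipping point: (0.528 - 0.403) / 0.12 = 1.0, or (0.528 - 0.355) / 0.12 = 1.4 to 1.5.

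The same formulas with 91(1 - m) completers per arm, over an assumed range of m, give these tipping points (points below the placebo mean, the two SEs as limits):

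| m | d 1.4, SD 3 | d 0.6, SD 1.3 |
|---|---|---|
| 5% | 8.7 to 9.6 | 3.7 to 4.0 |
| 12% | 2.5 to 3.5 | 1.0 to 1.5 |
| 20% | 0.7 to 1.7 | 0.3 to 0.7 |

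No matching figure is offered for CIBIC-Plus, because the documents give no category distribution.

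**The case against.** The strongest reply is that the SAP does still test the missing-data assumption. A reader might infer from Table 4 that neither co-primary has any such test. Table 5 and Section 5.4.2 show otherwise: both non-EMA primaries are repeated with control-based imputation, which is an MNAR analysis of exactly the endpoints that rest on MAR. Nor is it right that the EMA analyses get only a less conservative alternative. Their sensitivity analyses treat values after medication changes as MNAR, which enlarges the placebo-imputed set. This part of the reply stands. It does not cover dropouts classed MAR, or values worse than placebo.

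A marginal result does not by itself prove the need for a tipping point. A difference of 2.2 standard errors is 2.2 x 0.474 = 1.04. If all its dropouts are classed MNAR, the planned control-based run gives 0.88 x 1.04 = 0.918. That is below the fixed-SE threshold of 0.930, so the fragility would already show. Under the scaled SE (threshold 0.818) it would not. The example also depends on how the dropouts are classed.

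On disclosure, the summary of changes does mention a reduction and cites FDA correspondence, which is not available here. The ordering sentence in Section 7 follows text about primary analyses and may have been meant only for those. This softens the point but does not remove it. Table 4 lists sensitivity and supplementary analyses in separate rows, so a statement that supplementary analyses were reduced does not tell the reader that these two were dropped.

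Finally, a reader might want tipping points for both registrations. The protocol defines them only on the control-based imputation analyses, so asking for them on the MMRM and GLMM goes beyond its commitment.

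**Conclusion.** The point holds as a mismatch between protocol and SAP with a real loss of information. Two promised analyses per co-primary are absent and their removal is not named. Three consequences follow: no planned analysis goes beyond the placebo-mean or placebo-pattern assumption for dropouts; the reason-based MAR/MNAR classification in the EMA analysis is not tested in the adverse direction; and the protocol's rule for convincing MoCA benefit cannot be applied. The documents do not support the wider statement that missing data go unstressed, or that the change was wholly unrecorded.

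The size is illustrative. It assumes that every dropout is missing at Week 12, a simple two-mean estimator and the planning values. Subjects who stop drug are expected to keep attending visits, and SAP Section 5.3.5.1 includes their later data, so the missing fraction may be well under 12% and the result correspondingly more robust. At higher fractions a positive result could tip within a point of the placebo mean. The planned outputs would not show which case applies. Endpoints, sample size and primary tests are unaffected.

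**What to change.** - Restore to SAP Section 5.4.1 and Table 4, on the control-based EMA analyses, the tipping-point analysis and the all-missing-as-MNAR analysis for MoCA and CIBIC-Plus. Repeat the protocol's reading rule for MoCA.
- State which arm the all-MNAR run covers. For MoCA the protocol synopsis limits it to the E2027 group; Section 9.7.1.6.1 does not.
- Label the Table 5 cross-over analyses of the two co-primaries as missing-data sensitivity analyses, so that their role is clear.
- Correct Section 7 so that it no longer implies every pre-planned EMA analysis was kept. Name and justify any analysis that is still dropped.

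The cost is a few extra tables. The arm-specific MMRM fits and the two-step multiple imputation are already specified for the EMA primaries. The new work is a range of shifts and one reclassified run per endpoint.

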9.7.1.6.2 SECONDARY EFFICACY ANALYSES

The CGIC-DLB scale will be analysed as ordinal response data in a manner similar to the primary analysis of coprimary endpoint based on CIBIC-Plus. Other secondary endpoints are continuous variables and will be analyzed in a manner similar to the primary analysis of coprimary endpoint based on MoCA.

9.7.1.6.3 EXPLORATORY EFFICACY ANALYSES

The sleep endpoint (SCOPA-Sleep total score and subscores) will be analyzed in a manner similar to the coprimary endpoint based on MoCA.

If data permit, the relationship between E2027 PD effects on CSF cGMP (and other biomarkers) and various efficacy endpoints will be explored using correlation analysis and linear models will be fitted to further characterize the relationship between the changes in efficacy endpoints and the changes in E2027 PD variables as appropriate.

9.7.1.7 Pharmacokinetic, Pharmacodynamic, Pharmacogenomic, and Other Biomarker Analyses

9.7.1.7.1 PHARMACOKINETIC ANALYSES

The PK Analysis Set will be used for plasma E2027 concentration listings and for summaries of CSF E2027 concentrations by day.

A population PK approach will be used to characterize plasma E2027 PK. For this approach, PK data from this study will be pooled with existing data from Phase 1 studies. The effect of covariates on plasma E2027 PK, such as baseline characteristics/demographics, will be evaluated where feasible. Derived plasma E2027 exposure parameters, such as steady state area under the concentration time curve (AUC_{ss}) or average steady state concentration ($C_{ss,av}$)

will be calculated from the final PK model using the individual posterior estimates of the PK parameters and dosing history.

9.7.1.7.2 PHARMACODYNAMIC, PHARMACOGENOMIC, AND OTHER BIOMARKER ANALYSES

Pharmacodynamic Analyses

The PD Analysis Set will be used for the summaries and analyses of CSF PD biomarkers. The percentage change from baseline in CSF cGMP and any other PD biomarkers after at least 9 weeks of treatment with study drug postrandomization will be analyzed and presented graphically.

Pharmacodynamic/Pharmacokinetic Analyses

Data combining Phase 1 studies permitting, a population PK/PD approach will be used to characterize the relationship between plasma and/or CSF E2027 exposures and CSF PD biomarker levels. For this approach, data from this study will be pooled with relevant data from Phase 1 studies. The relationship between plasma and CSF E2027 exposure and the change from baseline of various efficacy endpoints will be explored graphically, as will the relationship between changes in CSF PD biomarkers and the change from baseline of various efficacy endpoints. Any emergent relationships will be explored through population PK/PD modeling.

The PK and PK/PD analyses will be detailed in a separate analysis plan and the results will be provided in a stand-alone report.

Pharmacogenomic Analyses

Pharmacogenomic analyses may be performed and reported separately. Details of these analyses, if appropriate, will be described in a separate analysis plan.

9.7.1.8 Safety Analyses

Evaluations of safety will be performed on the Safety Analysis Set. The incidence of AEs, out-of-normal-range laboratory safety test variables, abnormal ECG findings, and out-of-range vital signs, suicidality (C-SSRS), UPDRS-III, along with change from baseline in laboratory safety test variables, ECGs, and vital sign measurements (including orthostatic changes) will be summarized by treatment group.

